3.4. Statistical Analyses

Aim 1. Determine if improvement in depressive symptoms in caregivers of children with asthma predicts subsequent improvement in the child's asthma control. A CLPM for longitudinal data will be fit using a maximum likelihood SEM in order to explore reciprocal causation between asthma outcomes and depressive symptoms with lagged effect. A separate model will be constructed for each asthma outcome (e.g. CASI, ACT, steroid bursts). The full CLPM with all cross-lagged paths will test if both the asthma outcomes and depressive symptoms predict each other at subsequent visits. For each full model, paths will connect the value of the depressive symptom score (e.g. HRSD) at each visit to the asthma outcome (e.g. CASI) at each subsequent visit (e.g. 4 weeks later, 8 weeks later). Another set of paths will connect the asthma outcome at each visit to the HRSD at each subsequent visit. The full model will be compared to reduced models containing either the first set of paths or the second set. We hypothesize that the model with the first set of paths will provide a better fit than the second set. The models will be compared on goodness of fit criteria, a non-significant X^2 p-value .05 or more, fit indices .90 or more, RMSEA .05 or less, and significant path coefficients.⁶⁸⁻⁷⁵ Extensive overviews of the use of this CLPM for longitudinal data analyses are given by Cole and Maxwell and MacKinnon.^{70, 75} We will follow Cole and Maxwell's⁷⁰ guidelines for testing the proposed causal relationship, caregivers' depressive symptoms preceding child's asthma outcomes, with longitudinal data using SEM software *Mplus*. We will control for variables that might impact depressive symptoms or asthma response including age, gender and race/ethnicity. The primary analysis for this aim will use CASI scores for the child and caregiver HRSD scores. The HRSD is a widely used clinician-rated depression scale while the CASI scores take into account both asthma symptoms and asthma medication use to treat symptoms. Similar analysis will be conducted using the QIDS-SR as the depression measure and STAI as a caregiver anxiety measure. ACT scores and steroid bursts will be used as well as CASI scores in the analysis.

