Power: No data exist on which to base a power analysis. However, the hypothesis tests used here involve testing regression coefficients. To obtain an approximate idea of the power of our tests, we can refer to the test of a regression coefficient that can be detected with 80% power given a sample of 175. If we conservatively assume 10 predictors for the Primary Aim and Secondary Aim 2, then an effect size of $f^2 = 0.10$ could be detected. This effect size is classified as small ($f^2 = 0.02$) to medium ($f^2 = 0.15$) according to Cohen.⁶⁹ In the full model for Secondary Aims 1, 2 and 3 there are 13 measurement occasions and approximately 200 paths; however, the hypotheses to be tested involve the 78 paths between each visit and each later visit. Given this number of predictors to be tested, an effect size of 0.31 could be detected with 80% power. This effect size is classified as medium ($f^2 = 0.15$) to large ($f^2 = 0.35$) according to Cohen.⁶⁹

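### Aim 1's hypothesis ranks two non-nested models, which ignores the sign of the effect and favours the hoped-for model about half the time under no effect; the nested comparison the plan also describes is not made the decision rule

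*Combined protocol and SAP*

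**What the plan says.** Section 3.4, Aim 1, names HRSD and CASI as the primary pair. Paths run from HRSD at each visit to CASI at every later visit (first set) and from CASI to every later HRSD (second set).

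- Role of the full model: "The full CLPM with all cross-lagged paths will test if both the asthma outcomes and depressive symptoms predict each other at subsequent visits".
- Comparison: "The full model will be compared to reduced models containing either the first set of paths or the second set".
- Hypothesis: "We hypothesize that the model with the first set of paths will provide a better fit than the second set".
- Criteria for comparing models: a chi-square p-value of at least .05, then "fit indices .90 or more, RMSEA .05 or less, and significant path coefficients".
- The section also commits to published "guidelines for testing the proposed causal relationship". Those guidelines are cited but are not in the documents.

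The Power paragraph of 3.4 says "In the full model for Secondary Aims 1, 2 and 3 there are 13 measurement occasions and approximately 200 paths" and that "the hypotheses to be tested involve the 78 paths between each visit and each later visit". It gives a detectable effect of 0.31 at 80% power with 175 participants. A second figure, f² = 0.10, begins: "If we conservatively assume 10 predictors for the Primary Aim and Secondary Aim 2".

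Aims 3 and 4 reuse the Aim 1 approach.

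**The concern.** Call the model with only the HRSD-to-CASI paths A and the model with only the CASI-to-HRSD paths B. Aim 1 asks whether caregiver improvement is followed by improvement in the child's asthma. Whether A fits better than B is a different question, for three reasons.

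- A and B carry equal numbers of cross-paths and neither contains the other. With no effect in either direction, symmetry makes the ranking a coin toss.
- Fit does not depend on the sign of the paths. A model in which caregiver improvement precedes worse asthma fits as well as its mirror image.
- If depression affects asthma but asthma affects depression more strongly, B tends to rank first although the Aim 1 effect is real.

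The remaining criteria could rescue the aim if one were named as decisive. The visible text gives no difference test, no alpha for it, no required sign and no number of significant paths. The reading could therefore be chosen after the data are seen, on the primary analysis and again in Aims 3 and 4.

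**Working it through.** **1. The plan's own power figures.** Inputs from the Power paragraph: N = 175, 80% power. Alpha is not stated there; 0.05 is assumed. For a joint F test of u predictors, with df u and N − u − 1 and noncentrality f²N, solving for 80% power gives:

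- u = 10: f² = 0.098 (stated 0.10)
- u = 78: f² = 0.309 (stated 0.31)
- a single coefficient: f² about 0.045, which does not match

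So 0.31 describes a joint test of 78 predictors in one regression. In the Aim 1 model the 78 paths (1 + 2 + … + 12) are spread over 12 visit equations. For a 78-df likelihood-ratio test at 0.05, 80% power needs noncentrality 36.4; on the total scale that is 36.4/175 = 0.21, against 0.31.

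**2. Occasions and labels.** The Power paragraph counts 13 occasions: 13 × 12/2 = 78 paths. Table 2 has baseline plus 13, so 14 × 13/2 = 91. The paragraph refers to a Primary Aim and Secondary Aims 1 to 3, whereas 3.4 lists Aims 1 to 4, so it is unclear which figure belongs to Aim 1.

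**3. Degrees of freedom.** With 13 visits and two series there are 26 × 27/2 = 351 variances and covariances. With lag-1 autoregression (assumed; the plan states no order) the full model has 24 + 156 = 180 paths, 26 variances and 13 within-visit covariances, 219 in all. Its df is 351 − 219 = 132. A and B each drop 78 paths, so each has 210 df.

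**4. Simulation with no effect.** Assumptions: n = 175, 13 visits, autoregression 0.4, complete data, no covariates. Ranges span separate simulation runs.

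| Reading of the criteria | Support for Aim 1 |
|---|---|
| A ranks above B | 47–50% |
| Ranking + A meets limits + at least one or two significant paths | 41–43% |
| Ranking + limits + uncorrected full-versus-B test | about 6–8% |
| All 78 paths significant | 0% |

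At autoregression 0.6, with 14 visits, or with n = 149 (75.9% of 196, the retention quoted in 3.3.c.ii), the second row is 44–46%. The limits separate A from B poorly: both models meet them in about 68–71% of no-effect trials. One significant path is almost guaranteed: if the 78 tests were independent, 1 − 0.95^78 = 98.2%.

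**5. Sign.** With an assumed lag-1 effect of +0.08, the second reading gives support in 64% of trials; with −0.08, in 64–68%.

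**6. Reverse effect.** With autoregression 0.6, within-visit residual correlation 0.2, a true HRSD effect of 0.10 and a reverse effect of 0.15, A ranks first in 9.7% of 380 trials. The uncorrected test of the full model against B rejects in 78.4% of the same trials.

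**7. The nested test.** B is the full model without the HRSD-to-CASI paths, so this comparison addresses Aim 1 directly. At autoregression 0.4 with no effect, the uncorrected 78-df test rejects about 8–9%. With a Bartlett factor of n − 3 − k/2 per visit equation (k earlier visits) it rejects 4.5–5%. Requiring a positive sum of the HRSD-to-CASI coefficients as well gives 1.6–2.3% with no effect and at most 0.4% at −0.08. Power of the corrected test plus sign is 15% at a lag-1 effect of 0.05, 29% at 0.08 and 79% at 0.12.

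**The case against.** The ranking is not the whole rule. The sentence after the hypothesis lists fit limits and significant coefficients, in the plural, and the full model is compared with each reduced model. Read together these can give a false-support rate of 6–8%. The cited guidelines may name a test. Direction is stated in the aim itself and in the first hypothesis of 3.3.a.viii, and the Power paragraph claims only an approximate idea of power.

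Much of this stands, and it limits what can be said. A reader might infer that Aim 1 has a 50% false-positive rate; the documents do not support that, because 50% belongs to the ranking alone. A reader might also infer that the plan contains no usable test, but it describes the right nested comparison. Nor can a per-equation effect (0.21/12, about 0.017) be set against 0.31: the units differ.

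The plural does not rescue the rule, since requiring two significant paths still gives about 41%. The direction in the aim's wording does not enter any listed criterion. The guidelines cannot be checked here.

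The assumed autoregressive order also matters. With every autoregressive lag included the full model is saturated and its fit limits cannot fail. In a small check (60 trials per cell, 30% of variance stable between families), the uncorrected nested test rejected 22% with lag-1 fitted and 10% with lag-2. That is a reason to fix the order, not a defence of the ranking.

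**Conclusion.** The concern holds. The only hypothesis stated for Aim 1 is a ranking that does not answer the aim, and the other criteria do not repair it under a natural reading: about 41–43% support with no effect, irrespective of sign. Stricter readings give about 6–8% or less, and the visible text does not choose among them. The coin-toss result follows from symmetry and needs no simulation. The other percentages rest on assumed autoregression, lag-1 order, complete data and no covariates, because the documents give no HRSD–CASI values.

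The power mismatch is secondary: about 0.21 on the total scale against 0.31, with an occasion count and aim labels that do not agree with Table 2 and 3.4. A reader might infer that random intercepts must be a condition for support. That is a separate modelling question which the documents do not settle, and the point does not depend on it. This should be fixed before analysis.

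**What to change.** - Make one nested comparison the primary decision for Aim 1: the full model against the model without the HRSD-to-CASI paths, by joint likelihood-ratio test at alpha 0.05.
- State the number of occasions (78 df for 13, 91 for 14) and the autoregressive order, and name the small-sample correction in advance, for example Bartlett.
- Require in addition a positive sum of the HRSD-to-CASI coefficients (higher HRSD, higher later CASI).
- Report the reverse direction in the same way. Drop the A-versus-B ranking as a decision rule and keep the fit limits as model checks. A random-intercept model may be reported as a sensitivity analysis.
- Use the same rule for the other outcomes and in Aims 3 and 4, with the expected sign stated for each. For ACT it is negative, since 3.3.d.iv treats scores above 19 as controlled asthma.
- Restate the detectable effect for this test, and align the Power paragraph's aim labels and occasion count with 3.4 and Table 2.

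The cost is SAP wording and a few lines of code; no new data are needed. The joint test allows for delayed effects but has low power for small ones, about 30% at an assumed lag-1 effect of 0.08, and the plan should say so. The correction was checked on complete data only, so its behaviour under the planned full-information likelihood with missing visits should be checked before it is fixed.

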
The baseline assessment will take approximately 2.5 hours and will consist of a 45-60 minute structured clinical interview (SCID) using DSM-4 criteria to establish psychiatric diagnoses, depression, quality of life, and other assessments (see Table 2 for a complete list), as well as information about number of asthma-related hospitalizations, ER visits, and unscheduled clinic appointments by the child within the preceding 12 months as assessed by caregiver report (and confirmed through medical records when possible). Caregivers not meeting criteria for the intervention study will be paid for the initial assessment, informed of any psychiatric disorders identified (e.g. a psychiatric disorder other than MDD) and, when appropriate, given referral information. Caregivers with current MDD and meeting all inclusion criteria will be offered algorithm-based depression pharmacotherapy for 52 weeks. If a caregiver does not elect to participate in the algorithm-based treatment, they will remain eligible to enroll in the study and will receive referral information for an alternative depression treatment (e.g., psychotherapy) from a study psychiatrist. The caregiver will be still eligible to enroll in pharmacotherapy during a later stage of the study and will be advised by a study psychiatrist if they elect this option. Furthermore, participants who are currently receiving or plan to receive treatment for depression (e.g. medication, psychotherapy) by a healthcare provider outside of the study may also participate. In these cases the participants will receive all of the assessments and physician evaluation but will not receive algorithm-based treatment as part of the study. This protocol modification should improve enrollment by allow potential participants who prefer psychotherapy or want to receive antidepressant care from their PCPs to enroll. Given the inclusion, exclusion and discontinuation criteria, as well as the careful monitoring during the study this change should not adversely impact the safety profile of the study. The change is scientifically sound because the aims of the study are related to relationships between depressive symptom changes in the caregiver and asthma control in the child regardless of the method by which the changes were achieved. A total of 196 caregivers will be enrolled. A modified and simplified version the Texas Medication Algorithm Project (TMAP) MDD guidelines (Appendix 2) will be utilized to guide treatment. Caregivers and children will be assessed every four weeks (weeks 4, 8, 12, 16, 20, 24, 28, 32, 36, 40, 44, 48 and 52) with additional phone assessments 2 weeks after medication changes to assess for adverse events, medication side effects, or suicidality, and to confirm the next clinical appointment. Follow-up assessments will take approximately 1.5 hours including psychiatrist assessment and quality of life, asthma adherence, anxiety and depression questionnaires administered by a research team member. Caregivers will be assessed by a study psychiatrist at appointments for medication management. Caregivers will be paid \$60 for the baseline visit and assessments every 4 weeks (weeks 4-52). Children will be paid \$20 at each visit. Bus, rail, or taxi expenses will be reimbursed if these transportation methods are needed. Both caregivers and children will be paid using a UT Southwestern issued

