3.3.c.ii. Participant Enrollment: Dallas: The Dallas pediatric asthma clinic ([name]) that will be used for enrollment has 459 current active patients in the age range proposed for the study and 174 new patients in this age range each year. Given these numbers, if 26% of caregivers have current MDD (as in our pilot study) then over a 4 year enrollment period, we will have 300 eligible participants. To enroll 98 participants, 33% of these will need to agree to participate. We realize that enrollment is challenging in any clinical research study.

Furthermore, MDD rates could be lower than in our pilot, and participation rates could be less than 33%. Therefore, to augment enrollment at the Dallas site, we will use the Parkland COPC database to identify and contact potential participants. As of September 4, 2013, this database had 3500 children with asthma in the age range with 707 new patients entering the system each year. If, as in our pilot study, 26% of caregivers have current MDD, this potentially provides 1645 potential participants. Thus, if 6% of potential participants agreed, we could enroll 98 over 4 years. A study by Drs. [name] and [name] (co-Is) using this database to recruit girls ages 11-18 in a study about the human papilloma virus (HPV) vaccine employed similar recruitment methods to those in the proposed study. In this study from February and December 2011, the investigators evaluated 2160 Parkland COPC patient records, of which 875 (40.5%) appeared to be eligible. Of these 875, a total of 337 (38.5%) were enrolled. About 1.4% of recruitment letters were returned due to an incorrect address, in which case recruitment calls were still attempted. Over 3000 recruitment calls were made, with patient contact attempted an average of 3.7 times per patient. The 538 patients who did not complete the pre-clinic survey had the following study outcomes: unable to contact (19.1%), wrong number/out of order (10.7%), maybe later (14.2%), not eligible (11.4%), no-shows (9.8%), and not interested (6.5%). These data suggest that the database is a useful method for recruiting research participants and will supplement recruitment from the asthma clinic.

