Aim 2. Determine if improvement in depressive symptoms in caregivers of children with asthma predicts reduced unscheduled asthma-related service utilization. Separate analyses will be done for each event (ER visits, hospitalizations and unscheduled appointments). The dependent variable will be a count of the number of times the event occurred during the 52 week study period. This number will be converted to events per month to adjust for subjects who do not complete 52 weeks. The independent variables will be caregiver depressive symptoms as measured by HRSD along with site, baseline depressive symptoms, baseline asthma symptoms, and season of the year. Other baseline demographic and clinical variables (such as child's age) will be added if they improve the fit of the final model. Because the dependent variable is accumulated over the study period, caregiver HRSD will also be summarized over the study period for each subject by computing a seasonally adjusted slope of change over time during the 52 week study. All participants with two or more post-baseline HRSD measurements will be included in the analyses. Count data typically follow a Poisson distribution. Therefore, a generalized linear mixed model with Poisson link function will be used (SAS Proc GLIMMIX). Intercepts will be random effects. If an excessive number of subjects have zero events and the Poisson distribution is not appropriate (which often occurs with count data), then we will consider negative binomial models, zero-inflated Poisson models, and hurdle models. At times caregiver depression may get worse, despite treatment. Therefore, we will examine whether increases in caregiver depressive symptom severity predicts worse child asthma outcomes. The same model used above will be used here except that an indicator variable will be added to indicate if caregiver HRSD scores worsened or stayed the same during the study (zero or positive slope) versus improved (negative slope). The addition of this indicator variable will allow the relationship between change in HRSD and utilization events to differ for those who worsen or stay the same versus those who improve. This aim will be tested by the significance of this additional indicator variable. The primary analysis for this aim will use HRSD scores and ER visits (sensitive to the intervention in Pilot Study #2 and an important clinical outcome). However, similar analysis will be conducted using the QIDS-SR and STAI in place of the HRSD, and using unscheduled clinic visits and hospitalizations.

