Why was algorithm-based treatment selected? A randomized, placebo-controlled antidepressant trial was considered but rejected, in part because of the relative strengths of a clinical trial versus the experimental longitudinal within subject design described above in section 3.3.b. In addition, a lengthy placebo-controlled antidepressant trial would raise both safety and ethical concerns. Most importantly, our interest is not whether antidepressants work for MDD (this is already established) but whether improvement in caregiver depression has an impact on the child's asthma. A placebo-controlled design is not needed to observe a range of depression responses.

Non-pharmacologic interventions were considered. Brief interventions for depression are generally associated with small effect sizes.⁷⁹ Psychotherapy, while potentially very effective, requires more frequent and longer visits than pharmacotherapy. Another alternative design that we considered was treatment of the child's depression. Our pilot data suggest high rates of depression in the children with asthma as well as their caregivers. However, we rejected this approach because 1) of concerns regarding the safety of antidepressant treatment in children, 2) literature suggests that the impact of depression in children with asthma on asthma outcomes is largely mediated through caregiver depression,³⁶ and 3) a large depression study conducted as part of the STAR*D project observed that treatment of maternal depression was effective in treating depression in the child.⁸⁰ These findings suggest that a study addressing caregiver depression would have the greatest

clinical impact. Finally, an algorithm-based antidepressant treatment is desirable because it lends itself to primary care settings.

Why a 52-week period of antidepressant treatment? We observed positive changes in the child's asthma symptoms at 6 months in Pilot Study # 2. However, it may take some time for improvement in caregiver depression to result in improvement in the child's asthma control. In addition, to assess differences in relatively infrequent events (e.g. emergency care), 52 weeks may be needed. A period of 52 weeks 1) allows a preliminary determination of the impact of depression treatment on unscheduled service utilization, 2) allows a reasonable assessment of changes in the child's asthma control, and 3) allows us to assess the child's asthma through all four seasons.

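### Aim 1, and Aims 3 and 4 that reuse its method, should name season and site as covariates: Aim 2 already does, and either could distort the cross-lagged paths

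*Combined protocol and SAP*

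**What the plan says.** Section 3.4, Aim 1, fits a cross-lagged panel model in which paths run from the depression score at each visit "to the asthma outcome (e.g. CASI) at each subsequent visit (e.g. 4 weeks later, 8 weeks later"), with a second set of paths in the reverse direction. On the variables it says "The primary analysis for this aim will use CASI scores for the child and caregiver HRSD scores", and on covariates "We will control for variables that might impact depressive symptoms or asthma response including age, gender and race/ethnicity".

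Section 3.4, Aim 2, enters caregiver HRSD "along with site, baseline depressive symptoms, baseline asthma symptoms, and season of the year", and summarises HRSD by "computing a seasonally adjusted slope of change over time during the 52 week study".

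Aims 3 and 4 refer back to the Aim 1 method and add no covariates. Section 3.5 defends the 52-week period partly because it lets the team assess the child's "asthma through all four seasons". Nothing in the document carries season or site into the panel models.

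**The concern.** Aim 1 rests on temporal order: does HRSD at one visit predict CASI at a later one? There is no control group (section 3.3.b), so covariate adjustment is the main protection against a common cause that moves both series.

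Season is a candidate for such a cause. By naming season and seasonally adjusting the HRSD slope in Aim 2, the plan itself treats it as relevant to caregiver mood and to asthma events. Following each child through a full year observes season but does not adjust for it. Age, gender and race/ethnicity do not vary with the calendar, so they cannot stand in for it.

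Site works differently. It is fixed within a family, so it does not swing. If the two sites differ in average HRSD and average CASI, that stable difference can leak into the cross-lagged paths.

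At stake is a distorted lagged coefficient, inflated or reversed, in the primary analysis and in the quality-of-life and mediation analyses built on the same method.

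**Working it through.** **Inputs from the document**
- Analysis sample of 175 and 80% power; 10 predictors giving f² = 0.10; 78 tested paths giving f² = 0.31 (section 3.4, Power).
- Visits: "Caregivers and children will be assessed every four weeks" up to week 52, that is, baseline plus 13.
- Staggered entry. For Dallas the plan says "then over a 4 year enrollment period, we will have 300 eligible participants"; the Buffalo estimate uses the same period.

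**Assumptions.** Alpha is 0.05, since the Power paragraph gives none. Seasonal size, seasonal phase, autocorrelation and site differences are also assumed, because the document gives none of them.

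**Step 1: reproduce the plan's power figures.** Use the F test with u predictors, v = 175 − u − 1 and noncentrality λ = 175·f².
- u = 10, v = 164: at f² = 0.10, λ = 17.5 and power is 0.810. Power of exactly 80% needs f² = 0.098.
- u = 78 (13 × 12 / 2 visit pairs), v = 96: at f² = 0.31, λ = 54.25 and power is 0.802. Power of exactly 80% needs f² = 0.309.

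Both stated figures reproduce.

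**Step 2: can visit means absorb season?** Only if all families start on the same date. With a common start and seasonal amplitude 0.3 SD in both series, the false-positive rate was 5.5%. With entry spread over the year, each visit number mixes all seasons and the means no longer help.

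**Step 3: pooled lag-1 simulation with no true cross-effect.** Each series is noise plus an annual cosine; start dates are uniform over the year; there are 175 families and 14 visits. The fitted model is CASI(t+1) = visit effect + a·CASI(t) + b·HRSD(t), with family-clustered standard errors, and the test is of b = 0 at 5%. This is a stand-in for one lag-1 path, not the planned Mplus model.

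First structure: autocorrelation 0.6, same seasonal SD in both series (as a fraction of the non-seasonal SD), asthma lagging mood by 0 to 2 months, 400 runs per cell.

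| Seasonal SD | False positives, unadjusted |
|---|---|
| 0.1 | near 5% |
| 0.15 | about 6% to 14% |
| 0.2 to 0.3 | about 11% to 77% |

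For the 0.2 to 0.3 row, adding sine and cosine of visit date gave 4% to 7%.

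Second structure: half the variance a stable family trait, autocorrelation 0.4, 1,500 runs per cell. Here the seasonal size is the cosine *amplitude*; SD = amplitude/√2, so 0.3 is an SD of about 0.21.

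| Scenario | Unadjusted |
|---|---|
| No season, no site difference | 5.2% |
| Amplitude 0.15 in both, same peak | 5.3% |
| 0.3 in both, same peak | 9.2% |
| 0.3 in both, asthma peak 4 weeks later | 17.3% |
| 0.3 in both, asthma peak 13 weeks later | 25.9% |
| 0.3 in both, asthma peak 13 weeks earlier | 24.9%, all negative |
| Site difference 0.3 SD in both | 7.1% |
| Site difference 0.5 SD in both | 18.3% |
| Site 0.5 SD plus season 0.3, same peak | 30.4% |

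With season and site in the model, every row returned to 5% to 6.5%.

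**Step 4: closer to the planned test.** Wave-by-wave regressions with all-lag cross-paths, 13 visits, 300 runs per cell, no true effect, asthma lagging 0 to 2 months.
- Autocorrelation 0.6, seasonal SD 0.3: the joint test of the depression-to-asthma paths rejected in 12% to 22% of runs and the reverse set in 10% to 16%. The hypothesised set fitted better in 51% to 57%.
- The same with amplitude 0.3: joint rejection 5% to 9%.
- Half trait variance, autocorrelation 0.4, seasonal SD 0.3: 30% to 66%, the reverse set 27% to 46%, and the hypothesised set fitted better in 54% to 66%.

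**Step 5: cost of the added terms.** By the Step 1 formula at 175 families, detectable f² goes from 0.098 (10 predictors) to 0.106 (12) and 0.113 (14: site plus three season indicators). For the 78-path block with four extra covariates it goes from 0.309 to between 0.313 and 0.320, depending on how λ is defined.

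**The case against.** The strongest reply is that the Aim 1 sentence is open-ended. It promises control for variables that might affect depression or asthma and gives three as examples; Aim 2 shows the team counts season and site among such variables. A reader might infer that the plan excludes them. It does not: they are unnamed. What remains is that an open list is not a specified primary model, and the choice could be made after the results are seen.

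Second, the pooled lag-1 path is not the planned test. The plan estimates paths at every lag and compares the two directional sets on fit. A shared season tends to inflate both sets, so the comparison gives some protection; under the first structure it was close to a coin toss. This stands, and it rules out reading 77% as the error rate of the primary analysis or saying that season would look just like the hypothesised effect. The protection is partial, as the last case in Step 4 shows.

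Third, the document offers no evidence on how seasonal HRSD or CASI is, or which peaks first. This also stands. At small amplitudes there is almost no inflation, and if asthma peaks first the bias runs against the hypothesis.

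Fourth, site should not be charged to seasonal swings. Correct: it acts through stable level differences, and the document does not quantify any.

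**Conclusion.** The point holds as an inconsistency between aims that leaves a plausible bias open in the primary analysis. Season is named for Aim 2 and not for Aims 1, 3 and 4, and staggered entry prevents visit means from removing it. Site is a second, separate omission.

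The size is conditional. In the pooled lag-1 stand-in, bias is negligible at a seasonal SD of 0.1, modest at 0.15, and potentially large at 0.2 to 0.3 when asthma follows mood. A site difference of 0.3 to 0.5 SD in both variables gives about 7% to 18% false positives. For the planned all-lag test and the comparison of path sets, the inflation can be smaller and can affect both directions.

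The documents do not support a claim that the primary result will be false, or that the bias must favour the hypothesis. Confidence is medium: the textual gap is clear, but seasonal amplitude, phase and the site differences are all assumed.

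**What to change.** Add one sentence to the analysis plan for Aims 1, 3 and 4. It should commit to site as a covariate on all equations, and to calendar season at each visit (sine and cosine of visit date, or season indicators) as a time-varying covariate on both the caregiver measure and the child outcome, and in Aim 4 on the mediator as well. A site-by-season term can be listed as a sensitivity check, in case the annual pattern differs between Dallas and Buffalo.

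No new data are needed: Aim 2 already requires site and season, and season at each visit follows from the visit date. The price is a few extra parameters in an already large model and the small rise in detectable effect size shown in Step 5.
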